9. APPENDICES

9.1. Sample Size, Power, and Randomization

The sample size will be approximately 10 participants which will allow a general characterization of copper balance in response to ALXN1840.

9.2. Technical Specifications for Derived Variables

9.2.1. Adverse Events

The analysis of AEs is described in detail in Section 7.3.2.

Treatment-emergent AEs are events with start dates and start times on or after the date and time of the first study drug dose. If the start date of an AE is partially or completely missing and the end (stop) date and time of the AE does not indicate that it occurred prior to first dose, then the determination of treatment-emergent status will be based on the following:

- If the start year is after the year of the first study drug dose, then the AE is treatment-emergent; else,
- If the start year is the same as the year of the first study drug dose and
 - the start month is missing, then the AE is treatment-emergent; else if
 - the start month is present and is the same or after the month of the first study drug dose, then the AE is treatment-emergent; else,
- If the start date is completely missing, then the AE is treatment-emergent.

All other AEs are considered PTAEs (ie, AEs with partial or complete start dates before first study drug dose).

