Platelets	< 30,000 μL	None	Temporary interruption	Weekly repeat testing	At 15 mg QOD when platelets and other hematology parameters (neutrophils and hemoglobin) are at baseline concentration.
	> 30% ↓ from baseline	Platelets below reference range at baseline	Reduce dose to previous dose level if up-titration has occurred or reduce dose to 15 mg QOD if on 15 mg QD. No further dose ↑ until resolution of abnormality.	Weekly repeat testing	Not applicable.
Neutrophils	< 1.0 × 10 ³ /μL	None	Temporary interruption	Weekly repeat testing	At 15 mg QOD when neutrophils and other hematology parameters

Test	Result	Conditions	Action with ALXN1840 Dosing	Changes in Safety Monitoring ^a	Rechallenge ^{b,c,d}
					(hemoglobin and platelets) are at baseline concentration.
	> 30% ↓ from baseline	Neutrophils below reference range at baseline	Reduce dose to previous dose level if up-titration has occurred or reduce dose to 15 mg QOD if on 15 mg QD. No further dose ↑ until resolution of abnormality.	Weekly repeat testing	Not applicable.
Bilirubin	> 2 × ULN	Accompanied by ALT > 3 × ULN, indicative of liver injury	Temporary interruption	Weekly repeat testing	At 15 mg QOD or less frequent, when bilirubin is below ULN. Rechallenge under these conditions requires approval of the Alexion Medical Monitor.
Neurological assessment	Evidence of neurologic worsening by AEs or by neurologic physical exam assessment		Investigator and Alexion Medical Monitor will evaluate the need for dose modification (interruption, increase or decrease) based on copper control parameters and relevant clinical data. Rationale for dosing decision must be documented in study record and re-evaluated at the next study visit.	All neurologic worsening should be documented as AEs and followed up until study completion or resolution of symptoms.	Discuss with the Alexion Medical Monitor.

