8.3.1. Time Period and Frequency for Collecting AE and SAE Information

All AEs and SAEs will be collected from the signing of the ICF until the EOS Visit.

All SAEs will be recorded and reported to Alexion or the designee immediately and under no circumstance should this exceed 24 hours, as indicated in Section 10.3. The Investigator will submit any updated SAE data to Alexion within 24 hours of it being available.

Investigators are not obligated to actively seek AE or SAE data after conclusion of the study participation. However, if the Investigator learns of any SAE, including a death, at any time after a participant has been discharged from the study, and he/she considers the event to be reasonably related to the study intervention or study participation, the Investigator must promptly notify Alexion.

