10.3.1. Definition of AE

AE Definition

• An AE is any untoward medical occurrence in a participant, temporally associated with the use of study intervention, whether or not considered related to the study intervention.• Note: An AE can therefore be any unfavorable and unintended sign (including an abnormal laboratory finding), symptom, or disease (new or exacerbated) temporally associated with the use of study intervention.

Events Meeting the AE Definition

• Any abnormal laboratory test results (hematology, clinical chemistry, or urinalysis) or other safety assessments (eg, ECG, radiological scans, vital signs measurements), including those that worsen from baseline, considered clinically significant in the medical and scientific judgment of the Investigator (ie, not related to progression of underlying disease).• Exacerbation of a chronic or intermittent pre-existing condition including either an increase in frequency and/or intensity of the condition.• New conditions detected or diagnosed after study intervention administration even though it may have been present before the start of the study.• Signs, symptoms, or the clinical sequelae of a suspected drug-drug interaction.• Signs, symptoms, or the clinical sequelae of a suspected overdose of either study intervention or a concomitant medication. Overdose per se will not be reported as an AE/SAE unless it is an intentional overdose taken with possible suicidal/self-harming intent. Such overdoses should be reported regardless of sequelae.

Events Not Meeting the AE Definition

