 - The AE has a temporal relationship to the administration of the study intervention.
 - The event does not have a likely alternative etiology.
 - The event corresponds with the known pharmaceutical profile of the study intervention.
 - There is improvement on discontinuation and/or reappearance on rechallenge.
- The Investigator will use clinical judgment to determine the relationship.
- Alternative causes, such as underlying disease(s), concomitant therapy, and other risk factors, as well as the temporal relationship of the event to study intervention administration will be considered and investigated.
- The Investigator will also consult the IB and/or Product Information, for marketed products, in his/her assessment.
- For each AE/SAE, the Investigator **must** document in the medical notes that he/she has reviewed the AE/SAE and has provided an assessment of causality.
- There may be situations in which an SAE has occurred, and the Investigator has minimal information to include in the initial report to Alexion. However, it is very important that the Investigator always make an assessment of causality for every event before the initial transmission of the SAE data to Alexion.

Assessment of Causality

- The Investigator may change his/her opinion of causality in light of follow-up information and send an SAE follow-up report with the updated causality assessment.
- The causality assessment is one of the criteria used when determining regulatory reporting requirements.

Follow-up of AEs and SAEs

- The Investigator is obligated to perform or arrange for the conduct of supplemental measurements and/or evaluations as medically indicated or as requested by Alexion to elucidate the nature and/or causality of the AE or SAE as fully as possible. This may include additional laboratory tests or investigations, histopathological examinations, or consultation with other health care professionals.
- If a participant dies during participation in the study or during a recognized follow-up period, the Investigator will provide Alexion with a copy of any post-mortem findings including histopathology.
- New or updated information will be recorded in the originally completed CRF.
- The Investigator will submit any updated SAE data to Alexion within 24 hours of receipt of the information.

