7.3.2. Adverse Events

The verbatim terms as reported in the CRF by Investigators to identify AEs will be coded using MedDRA Version 22.0 or higher and summarized by primary SOC and PT.

Adverse event toxicity will be evaluated using the National Cancer Institute (NCI) Common Terminology Criteria for Adverse Events (CTCAE) Version 5.0 (published 27 Nov 2017).

Adverse event causality is determined by the Investigator using the following assessment categories: unrelated, or related.

Treatment-emergent AEs are defined as those AEs with onset on or after the first dose of treatment (ie, study drug). Events reported with a partial onset date (eg, month and year are reported but the day is missing) will be considered to be treatment-emergent if it cannot be confirmed that the event onset was prior to the first dose of study drug based on the available date entries.

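### The TEAE definition has no worsening clause, so an adverse event that starts before Day 1 and worsens on ALXN1840 may be counted only as pre-treatment

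*SAP*

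**What the plan says.** The SAP defines treatment-emergent AEs in two places, both by onset. SAP 7.3.2: "Treatment-emergent AEs are defined as those AEs with onset on or after the first dose of treatment". SAP 9.2.1, the derivation: "Treatment-emergent AEs are events with start dates and start times on or after the date and time of the first study drug dose". Neither has a criterion for a change in severity or seriousness. SAP 9.2.1 then assigns all remaining AEs to the PTAE category. The protocol names TEAEs as a safety endpoint but does not define them, so the SAP rule is the only one.

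Events before dosing are on the AE form. Protocol 8.3.1: "All AEs and SAEs will be collected from the signing of the ICF until the EOS Visit". The Schedule of Activities opens screening at Day -42.

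On follow-up, Protocol 10.3.3 says: "New or updated information will be recorded in the originally completed CRF".

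Two other places treat worsening as an AE. Protocol 10.3.1 lists, among events that meet the AE definition, "Exacerbation of a chronic or intermittent pre-existing condition including either an increase in frequency and/or intensity of the condition". Protocol Table 7 (Section 6.6) says "All neurologic worsening should be documented as AEs and followed up until study completion or resolution of symptoms", and has a similar instruction for psychiatric worsening.

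**The concern.** A TEAE table should show what began or got worse on drug. An onset-only rule captures the first and leaves the second to the way the site fills in the form. If a grade increase is entered as an update to an existing record, the record keeps its pre-dose start date and the rule returns PTAE.

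The gap matters in this trial because the pre-dose period is not quiet. Zinc is stopped by Day -21 and chelators on Day -4, so some participants may reach Day 1 with ongoing symptoms already on the AE form. Protocol Table 3 lists neurological worsening from copper mobilization as a potential risk of the drug and relies on monitoring of neurologic AEs to detect it. If such worsening sat under a pre-treatment heading, the TEAE tables would understate what happened on drug, in the drug's favour. SAP Section 4 says that the interim analyses support regulatory submissions.

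**Working it through.** The plan states no figure on this point, so there is nothing to reproduce. The check applies the rule to simple cases, compares the recording instructions, and then works out the weight of one participant.

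**Step 1: the rule applied.** For complete dates, SAP 9.2.1 reduces to: start at or after first dose = TEAE, otherwise PTAE. The courses below are illustrations.

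| Course | Records and start days | Result |
|---|---|---|
| Grade 1 from Day -3, Grade 3 on Day 5, entered as an update | one: Day -3 | PTAE |
| Same course, worsening entered as a new AE | two: Day -3 and Day 5 | PTAE and TEAE |
| Starts on Day 5 | one: Day 5 | TEAE |

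The first two rows are the same clinical course. Only the way it is recorded differs.

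**Step 2: which record do the documents call for?**
- Protocol 10.3.3 directs new information to the original entry. It does not mention grade, onset date or a new record.
- Protocol 10.3.1 makes exacerbation of a pre-existing condition an AE. A condition held only as medical history has no AE record, so its exacerbation needs a new entry with a post-dose start and is a TEAE. For a condition already on the AE form since screening or run-in, the text does not say whether to open a second record.
- Table 7 requires neurologic and psychiatric worsening to be documented as AEs. It is likewise silent on whether an AE already open gets a second record.

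Both ways of recording are therefore compatible with the text.

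**Step 3: where the first course would appear.** It would be in the PTAE outputs (SAP 7.3.2.1 and 7.3.2.2). It would be missing from the TEAE tables by SOC and PT (7.3.2.2 to 7.3.2.4), by relationship (7.3.2.5) and by toxicity (7.3.2.6). The rule of taking the highest toxicity in 7.3.2.6 does not rescue it, because that rule works only within TEAEs.

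**Step 4: weight of one participant.** Formula: 100/N percentage points. SAP 9.1 gives N as approximately 10.
- N = 8: 100/8 = 12.5
- N = 10: 100/10 = 10.0
- N = 12: 100/12 = 8.3

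This assumes that the participant has no other TEAE in the same table row. Within a cohort the denominator is smaller and the weight larger; the documents give no cohort sizes.

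**The case against.** The strongest reply is that no text says worsening is absorbed into the old record. The sentence in Protocol 10.3.3 sits among follow-up duties such as supplemental tests, post-mortem findings and SAE updates, and the CRF completion instructions are not part of the documents. Protocol 10.3.1 and Table 7 can be read as calling for a new AE, which the present rule would count as a TEAE.

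Nor would the event vanish. PTAEs have their own summary, SOC/PT table and listing. The listings of SAEs and of AEs leading to withdrawal or death are not limited to TEAEs (SAP 7.3.2.1). Laboratory worsening appears in the CTCAE shift tables (SAP 7.3.3.1), and QTc worsening in the ECG summaries (SAP 7.3.3.4). The safety analysis is descriptive, and with about 10 participants the listings can be read case by case. Other defaults push TEAE counts up: uncertain start dates mostly resolve to treatment-emergent (SAP 9.2.1), and a missing relationship is taken as related (SAP 7.3.2.5).

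All of this stands, and it limits the point to what may happen. It does not supply the missing rule: whether an on-drug worsening is a TEAE still depends on the site's recording habit. The listings and shift tables mitigate only in part, because symptoms such as tremor or low mood have no shift table, and a reader of the TEAE tables would not see the on-drug grade.

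**Conclusion.** The point holds as a gap in a stated rule. The SAP has no worsening clause and the documents do not settle how worsening of an open AE is recorded. An AE with onset between consent and first dose that rises in grade or becomes serious on ALXN1840 may therefore be missing from the TEAE, related-TEAE and toxicity tables. Each participant affected changes a TEAE percentage by about 10 points at N = 10, subject to the single-event assumption above. The number affected cannot be estimated from the documents.

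Three stronger readings are tempting and not supported:
- That every such event is left out of the TEAE tables. This follows only if the worsening is entered as an update; entered as a new AE, it is a TEAE.
- That neurologic worsening in particular would be lost. Table 7 requires it to be documented as an AE, which may well produce a new record.
- That the pre-dose window is at least as long as dosing, so that much of the AE data is at risk. The 42 days are a maximum, since the screening window runs from Day -42 to Day -9. The planned 39 dosing days can become 39 + 14 = 53 if the Outpatient Period is extended. Window length also says nothing about how often events worsen.

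This should be corrected before the TEAE tables are produced. It does not touch the copper balance analyses.

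**What to change.** In SAP 7.3.2 and 9.2.1, define a TEAE as an AE with onset on or after first dose, or with onset before first dose that increases in CTCAE grade or becomes serious on or after first dose. Grade it at its on-treatment maximum.

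So that the change can be dated, state in the CRF instructions that such worsening is entered as a new AE record starting on the date of worsening.

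The two changes together could count one episode twice, so add a rule: the original record stays a PTAE at its pre-dose grade, and the worsened episode is counted once as a TEAE, through the new record.

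The cost is a clause in each of two SAP sections, the counting rule and one CRF instruction. TEAE counts may come out slightly less favourable.

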9.2.2. Age and Dates

Age will be presented as the number of years between date of birth and the reference date. The following age in Table 2 may be computed, with reference date indicated.

Table 2: Age and Reference Date

Age	Reference Date
• Age at Enrollment	• Date of informed consent

The following formula should be followed for calculation of age if needed:

$$\text{Age (year)} = \text{FLOOR}(\text{reference date} - \text{date of birth})/365.25$$

where FLOOR() function returns the integer part of the result.

In cases where only the month and year are provided for a date, the day for the date will be imputed as 15. Missing month will be imputed as June. In cases where the day is observed but the month is missing, the date will be imputed as June 15. In instances when the imputed reference date is earlier than the birth date, the birth date will be used as the reference date.

9.2.3. Analysis Relative Day

Analysis relative day is the day relative to the first dosing day. It will be calculated as: analysis date – first dose date + 1 if analysis date is after the first dose date, or else as: first dose date – analysis date.

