 - Day 1 through Day 8 (Input/Output (I/O) for 15 mg)
 - Day 25 through Day 39 (Days 25 through 28, I/O for 15 mg; Days 29 through 39, I/O for 30 mg)

5. During these periods all intake (including food and drink) and output (including urine and feces) will be collected and assessed for copper and molybdenum.

Abbreviations: AP = accumulation period; EOS = End of Study; SS = steady state.

Participants who are taking copper-chelating therapies (penicillamine or trientine) at the time of enrollment will be discontinued from their decoppering therapies starting on Day -4 to allow a Baseline assessment of copper/molybdenum balance prior to ALXN1840 treatment. On Day 1, participants will be initiated on 15 mg/day of ALXN1840 for a Treatment Period of approximately 28 days followed by titration up to 30 mg/day on Day 29. Before titration to 30 mg/day, the SRC will review available safety data through Day 23 for each participant.

Participants will have intake and output collection periods from Day -4 through Day -1, from Day 1 through Day 8, and Day 25 through Day 39. The collection periods will support an assessment of both copper and molybdenum balance (as a measure of ALXN1840 absorption, distribution, metabolism, and excretion [ADME]) at the 15 mg and 30 mg doses and will allow assessment of the effects of duration of treatment on copper elimination and copper balance.

Collection periods for feces and urine will vary in duration from 3 to 15 days to support assessment of both copper and molybdenum balance before and at steady state for both 15 mg and 30 mg. Equilibration periods on copper/molybdenum-controlled diets will be a minimum of 48 hours. Copper balance will be calculated as the mean daily copper balance over each of the 4 collection periods. The interpretation of copper balance will be based on the criteria established by Hill (1986) when undertaking copper balance studies with zinc treatment. For assessment of ALXN1840 effect on copper balance, the time period for analysis will take into consideration the average bowel transit of approximately 40 hours (male: 33 hours; female: 47 hours) (Camilleri, 1986; Metcalf, 1987).

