7.2. Efficacy Analyses

The analyses and summaries will be based on the FA Set. For by-visit analyses, the definition is given in Appendix 9.2. Listings will also be provided for all efficacy assessments.

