7.2.1. Primary Analysis

Based on the ALXN1840 mechanism of action, the primary objective of this study is to demonstrate a net negative copper balance with daily repeat-dose ALXN1840 treatment (15 mg and 30 mg) in participants with WD.

The primary analysis will be performed using the FA Set. Average daily copper balance and molybdenum balance will be calculated over the following periods:

- Day -4 through Day -1 representing pre-dose Baseline
- Days 1 through 8 representing the ALXN1840 15 mg/day accumulation period
- Days 25 through 28 representing the ALXN1840 15 mg/day steady-state period
- Days 31 through 35 representing the ALXN1840 30 mg/day accumulation period
- Days 36 through 39 representing the ALXN1840 30 mg/day steady-state period

Copper balance is defined by the difference in copper input and copper output. A negative Copper balance will indicate greater copper output than copper intake. Copper input is defined as the sum of all copper input as measured in all food and fluids over the specified period. Copper output is defined as the sum of all copper output as measured in urine and feces over the specified collection period. Many of the copper inputs and outputs will be collected with technical replicates and the mean of the replicates will be utilized in the analysis. The average daily copper balance is calculated as the difference in copper input and copper output during the specified period, divided by the total number of days in that period.

As ALXN1840 is expected to increase copper excretion through fecal excretion, copper in stool will be critical for determining copper balance. Because the timing of bowel movements can be irregular, assessment of copper and molybdenum balance will only include data up to the day of

the final bowel movement. For example, if the participant does not have a bowel movement on Day 8, then average daily copper balance for the Day 1 through Day 8 period will only include data from Day 1 through Day 7.

In the case of the 15 mg/day steady-state period (ie, Day 25 through Day 28), stool data collected on Days 29 - 30 samples may be used if needed to support assessments for the 15 mg/day dose. Use of these stool data (as needed) are consistent with an approximately 2-day gastrointestinal transit time.

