9.2.8. Visit Windowing

In analysis of data summarized by study visit, all data collection will be reassigned a study visit where data is scheduled for collection based on the actual days relative to Baseline. All visits will be assigned a target study day. Baseline will have a target study day of 1. For each assessment, the post-Baseline Period will be divided up using the scheduled visit's target day. The lower bound of each visit interval will be evaluated as the mid-point between the target day and the previous visit's target day in the following manner: $\text{study day interval lower bound} = \text{ceiling}(\text{target study day} - ((\text{target study day} - \text{last target study day})/2))$. [Table 3](#) shows an

example of visit windowing that will be used to summarize by-visit vital sign data. Other data will be summarized similarly in accordance to their SoA (**Protocol Table 1**).

Table 3: Visit Windows used to Summarize by-Visit Vital Signs Data

Scheduled Visit	Target Study Day	Study Day Interval
Baseline	1	Last measurement on or prior to first dose of study drug
Day 9	9	2 to 15
Day 23	23	16 to 31
Day 40	40	32+

If more than one value is mapped to the same scheduled visit, the closer of those values will be considered for summarization. If multiple records exist with the same distance from the target study day, the last occurrence will be used. Visit windows are intended to be contiguous such that all data collected at all post-Baseline visits, whether scheduled or unscheduled, will map to one of the visits.

The visit displayed on data listings will be reflective of the scheduled visit label as reported on the CRF. Study days relative to Baseline will be displayed for each visit so it is apparent which visit the data may have been reassigned to in the summaries.

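### The SAP 9.2.3 relative-day formula is wrong as written: run-in Days -4 to -1 come out as 4 to 1 and the first-dose day as 0, contradicting the numbering used elsewhere in the SAP

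*SAP*

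**What the plan says.** SAP 9.2.3 derives relative day in two branches, which meet at the words "after the first dose date, or else as: first dose date – analysis date". In full, the first is "analysis date – first dose date + 1 if analysis date is after the first dose date". The second covers every remaining date: "or else as: first dose date – analysis date". This is the only relative-day derivation in the SAP.

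Other sections fix the numbering that the analysis needs:

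- SAP 4: "On Day 1, participants will be initiated on 15 mg/day of ALXN1840".
- SAP 7.2.1, baseline balance period: "Day -4 through Day -1 representing pre-dose Baseline".
- SAP 7.2.1, first treatment period: "Days 1 through 8 representing the ALXN1840 15 mg/day accumulation period".
- SAP 9.2.8: "Baseline will have a target study day of 1".

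SAP 7.2 points to the appendix that contains the formula: "For by-visit analyses, the definition is given in Appendix 9.2". SAP 9.2.8 assigns visits by actual days relative to Baseline and says that such days will be shown in the data listings. SAP 7.2.1 lists the balance periods by day number but does not cite 9.2.3.

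**The concern.** The formula has two faults. The subtraction in the second branch is reversed, so a pre-dose date gets a positive number. The first branch applies only to dates strictly after first dose, so the first-dose date drops into the second branch and gets 0. The rule can return neither a negative day nor Day 1 for the first dose.

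The run-in exists to separate untreated from treated copper balance, and the change from that baseline is a secondary endpoint (SAP 5.1.2 and 7.2.2). A day variable that gives run-in and treatment days the same numbers cannot keep the two apart. In listings, if the displayed study day comes from 9.2.3, a reader could not tell from the number whether a record was before or on treatment.

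**Working it through.** **Inputs.** The two branches are from SAP 9.2.3 and the windows from SAP 7.2.1. First dose is Day 1 (SAP 4). There is no Day 0 in the protocol numbering. Admission is Day -8, and intake and output are collected on Days -4 to -1, 1 to 8 and 25 to 39 (Protocol 1.2 and 4.1).

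**Formulas**, with A the analysis date and D the first dose date:

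- As written: A - D + 1 if A > D; otherwise D - A.
- Conventional: A - D + 1 if A >= D; otherwise A - D.

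| Protocol day | A - D | As written | Conventional |
|---|---|---|---|
| -8 | -8 | 8 | -8 |
| -4 | -4 | 4 | -4 |
| -3 | -3 | 3 | -3 |
| -2 | -2 | 2 | -2 |
| -1 | -1 | 1 | -1 |
| 1 (first dose) | 0 | 0 | 1 |
| 2 | 1 | 2 | 2 |
| 4 | 3 | 4 | 4 |
| 8 | 7 | 8 | 8 |
| 40 | 39 | 40 | 40 |

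The formula as written does not reproduce the SAP's own Day -4 to -1 or Day 1. Each value from 2 to 8 is shared by a pre-dose day and a treatment day. The value 1 belongs only to Day -1, an untreated day.

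**Effect on the windows, if they were selected with this variable:**

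| Window | As written | Conventional |
|---|---|---|
| -4 to -1 | no days | Days -4 to -1 |
| 1 to 8 | Days -8 to -1 and 2 to 8 | Days 1 to 8 |
| 25 to 28 | Days 25 to 28 | same |
| 31 to 35 | Days 31 to 35 | same |
| 36 to 39 | Days 36 to 39 | same |

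The written rule puts 8 + 7 = 15 calendar days in the 1 to 8 window. Of these, 4 + 7 = 11 have intake and output collection.

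**Size of any distortion in the Day 1 to 8 mean.** Let b be the untreated daily balance and e a constant daily treatment effect (an assumption). The 11 collection days sum to 4b + 7(b + e) = 11b + 7e.

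- Divided by 11: b + (7/11)e, so the effect appears at 64%.
- Divided by the stated 8 days: (11/8)b + (7/8)e, so the effect appears at 88% and the untreated balance is inflated to 138%.

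SAP 7.2.1 divides by the number of days in the period and does not settle which count would apply here.

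**Calendar days and the Outpatient Period.** The Outpatient Period may be extended by up to 14 days, after which the participant resumes at Day 23 (Protocol 4.1 and Table 4; SAP 4). With a 14-day extension it runs to calendar Day 22 + 14 = 36, and protocol Day 25 falls on calendar Day 25 + 14 = 39. Calendar Days 25 to 28 are then outpatient days without collection. Calendar Days 36 to 39 contain one collection day, protocol Day 25, which is still on 15 mg/day. So for this participant even the conventional formula would not select the intended balance periods.

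**The case against.** The strongest reply is that the SAP never says that the balance periods are built from this variable. SAP 7.2.1 names them by study day without citing 9.2.3. The pointer in SAP 7.2 concerns by-visit analyses, and a collection period is not a visit. SAP 9.2.8 divides up only the time after Baseline. The rule that an extended participant resumes at Day 23 makes sense only with protocol days. If nominal days are used, all four run-in days are kept and nothing overlaps. This stands, so the empty window and the mixed Day 1 to 8 window are conditional.

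A reader might also infer that every change from baseline would be set to missing under SAP 9.2.6. The documents do not support that. SAP 9.2.4 and the Baseline row of SAP Table 3 take the last value on or before first dose, which is a date comparison and needs no day number. Treatment-emergent status (SAP 9.2.1) also compares dates and times directly. Only the change in balance from the run-in period is exposed.

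Finally, the intended numbering is clear from the rest of the SAP, an empty baseline would show at the first run, and the study is descriptive with no hypothesis test. Undetected bias is therefore unlikely. That limits the seriousness but does not correct the formula: two programmers working independently from the written text would agree on the wrong numbers.

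**Conclusion.** SAP 9.2.3 is wrong as written. That rests only on the sentence itself and on SAP 4, 7.2.1 and 9.2.8, and no other section corrects it. It looks like a drafting slip in an operative derivation rule, and it should be corrected.

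The consequences come at two levels, each with its own assumption:

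- If the listings take their study days from 9.2.3, those days are ambiguous for values 2 to 8 and wrong for Day -1 and the first-dose day.
- If the balance periods are also selected with 9.2.3, the baseline period has 0 of 4 days, the change in copper balance from run-in cannot be computed, and the Day 1 to 8 period mixes run-in days with Days 2 to 8 and omits the first-dose day.

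A reader might infer one fixed dilution of the treatment effect, such as 64%. The documents do not support a single figure, because it depends on which days enter and on the divisor. The three later treatment periods, including both steady-state periods, are untouched by this error.

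**What to change.** Replace the rule in SAP 9.2.3 with: relative day equals analysis date minus first dose date plus 1 if the analysis date is on or after the first dose date; otherwise analysis date minus first dose date, which is negative, with no Day 0. This returns Days -4 to -1 and Day 1 as the other sections need them and removes all duplicate numbers.

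Add one sentence to SAP 7.2.1 stating that the balance periods are selected by protocol (nominal) day, not by calendar relative day, so that participants with an extended Outpatient Period are assigned correctly.

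The cost is two sentences in the SAP. No design feature, data collection or clinical procedure changes. Any program that already implements the written formula would need to be checked and rerun.
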